8 RESEARCH METHODS

8.1 Study Design

This is a multi-centre, observational, non-comparative, retrospective cohort study designed to evaluate the long-term safety and effectiveness of osilodrostat in non-CD CS patients. Patients treated with oral osilodrostat regardless of the duration of their treatment will be followed retrospectively for up to 36 months after initiating osilodrostat. Follow-up for each patient will be variable, rather than fixed. Using a variable follow-up, rather than a fixed follow-up period for each patient, maximises the

Final v2.0 33 of 63 18 April 2023

person-time of patient follow-up in the study. This methodological approach allows for increased precision of findings compared to a fixed follow-up period because the unit of observation in analyses is person-time accrued aggregately across all eligible patients, rather than a count denominator of patients exposed to osilodrostat. Robust statistical properties are also associated with this study design feature.

Participating institutions will be where the past treatment of patients took place using osilodrostat under ATU and/or as a part of routine clinical practice. Data will be abstracted from patients' existing electronic, or paper institutional medical records collected during the French ATU and/or routine clinical care. Importantly, the historical decisions of health care providers (HCPs) to treat patients with osilodrostat were made purely at the discretion of the treating physicians as discussed with their patients. Thus, there is no relationship between the decision to treat patients with osilodrostat and inclusion in this study.

The study schematic is presented in Figure 1 below and illustrates the dates corresponding to the study's retrospective follow-up period, the French ATU, the latest date an osilodrostat-treated patient is eligible for inclusion in the cohort study, and general timelines.

Final v2.0 34 of 63 18 April 2023

***at every 12 weeks until the earlier LFTU, death, or the end of the retrospective follow-up period or treatment discontinuation

Figure 1. Study Schematic

Abbreviations: ATU: Autorisation Temporaire d'Utilisation.; F/U: Follow Up; LTFU: Lost to Follow Up.

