The follow-up period will be variable, from the start of their osilodrostat onset period until the earlier of loss to follow-up, death, the end of the retrospective follow-up period or treatment discontinuation occurs. The patients with a potential follow-up of at least 12 weeks will be part of the primary analysis. The only patients excluded from the primary efficacy analyses will be the ones who started treatment with osilodrostat less than 12 weeks prior to the end of the abstraction period, and are still treated with osilodrostat at the end of the abstraction period. These patients will be included only in the analyses of the secondary and exploratory endpoints including safety. The patients who discontinued treatment for any reason or were lost-to-follow up prior to 12 weeks will be considered non-responders for the primary endpoint. The end of study is defined as the last available assessment after treatment initiation for the last patient.

The timing of data collection is summarised in the Figure 1/Table 2

Final v2.0 36 of 63 18 April 2023

Table 2 Data Collection Schedule

	Data Collection Points							
Assessment	BLa	Wk 4 ^b	Wk 8 ^b	Wk 12 ^b	Wk 18 ^b	Wk 24 ^b	Wk 36 and every 12 wks until death, loss to F/U or end of patient data collection*	
Window period		± 2	± 2	± 4	± 2	± 4	± 4 wks	
		wks	wks	wks	wks	wks		
Authorisation of access to patient's data for enrollment ^c	X							
Inclusion-Exclusion Criteria	X							
Demographics (age at diagnosis of CS, gender)	X							
BMI	X	X	X	X	X	X	X	
Clinical (disease) characteristics including date of diagnosis	X							
Medical and surgical history ^h	X ^g							
CS-Specific Physical Exam Findings (after BMI per every visit) [@]	X	X	X	X	X	X	X	

ECIOPP-RECAG-IVI-0390	Data Collection Points						
Assessment	BLa	Wk 4 ^b	Wk 8 ^b	Wk 12 ^b	Wk 18 ^b	Wk 24 ^b	Wk 36 and every 12 wks until death, loss to F/U or end of patient data collection*
Window period		± 2 wks	± 2 wks	± 4 wks	± 2 wks	± 4 wks	± 4 wks
Vital signs (blood pressure)	X	X	X	X	X	X	X
Electrocardiogram	X	X	X	X	X	X	X
Prior CS treatment(s)	X						
Prior medications ^e	X ^g						
Concomitant medications	X ^g	X	X	X	X	X	X
Osilodrostat initiating dose (date) ^d	X	X	X	X	X	X	X
Up /or down- titration regimen for Osilodrostat (date) ^d		X	X	X	X	X	X
Comprehensive Metabolic Panel (CMP&), Complete Blood Count (CBC*), lipids [§]	X	X	X	X	X	X	X
HBA1c	X	X	X	X	X	X	X

	Data Collection Points						

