- f. Baseline mean urinary free cortisol data can be collected within 1 month prior to osilodrostat initiation.

Final v2.0 40 of 63 18 April 2023

g. Footnote-a is not applicable to the following assessments: prior medications, concomitant medications, medical and surgical history, and mean urinary free cortisol.

- h. All available medical history and surgical history related to CS must be collected. Medical and surgical history not related to CS that occurred within 6 months prior to the first dose of Osilodrostat must be collected.
- *End of data collection may be due to earlier of loss-to-follow-up, death, end of retrospective follow-up period or treatment discontinuation

*CBC includes WBC, RBC, Haemoglobin, Haematocrit, MCV, MCH, MCHC, RDW, Platelet Count, MPV and Differential (Absolute and Percent - Neutrophils, Lymphocytes, Monocytes, Eosinophils, and Basophils)

&CMP includes Albumin, Alkaline Phosphatase, ALT, AST, Calcium, Carbon Dioxide, Chloride, Creatinine with GFR Estimated, Glucose, Potassium, Sodium, Total Bilirubin, Total Protein, (Blood) Urea Nitrogen

\$Lipid variables include Total Cholesterol, HDL, LDL, and Triglycerides

[@]For list of CS-specific examination findings, please refer to 8.3.2.

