8.7.9 Analysis of Secondary Endpoints

Changes from baseline for biochemical variables and clinical outcomes to Week 4, 8, 12, 18, 24, 36, and to every 12 weeks until the earlier of loss to follow-up, death, or the end of the retrospective follow-up period or treatment discontinuation will be summarised descriptively and provided as listing.

Final v2.0 50 of 63 18 April 2023

Baseline is defined as the available value at the time of osilodrostat initiation or the closest value within 2 weeks prior to osilodrostat initiation. Change from baseline will be calculated as the visit value of interest minus the baseline value.

For secondary variables, refer to Table 1.

Change from initial dose

The extent of exposure will be provided by summarising the description of initiating dose (and date) of osilodrostat, and up- and/or down-titration regimen (dose increases/decreases, date).

Proportion of patients who experienced TEAEs and AESIs

An overall summary table of all treatment-emergent adverse events (TEAEs) will be presented with the number and proportion of participants and the number of events. Summary incidence tables of all TEAEs (through Week 12 and follow-up at every 12 weeks until the earlier of loss to follow-up, death, or the end of the retrospective follow-up period, or treatment discontinuation), SAEs and TEAEs by severity grade and relationship to study drug will be provided, classified by primary System Organ Class (SOC) and Preferred term (PT).

All AEs will be coded according to the latest version of the Medical Dictionary for Regulatory Activities and will be classified by MedDRA PT and SOC.

All safety data will be included in the participant data listings, such as listings of all TEAEs, SAEs, TEAEs leading to study drug withdrawal and listings of deaths.

Summary incidence tables of select AEs specific to CS (AEs of fatigue, nausea, vomiting, headache, backache, oedema, clinical features including acne, hirsutism, laboratory abnormalities including hypokalaemia or hyperkalaemia, and hypertension) by severity grade and relationship to study drug will be provided, classified by primary SOC and PT.

Adverse Events of Special Interest (AESI) will be defined as following AEs:

Final v2.0 51 of 63 18 April 2023

Adrenal hormone precursor accumulation-related AEs

- - o Hypocortisolism-related AEs
 - o Pituitary tumour enlargement-related AEs
 - o Arrhythmogenic potential and QT prolongation AEs

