10.1 Definitions

Adverse events (AEs)

An AE is any untoward medical occurrence in a patient or clinical study participant administered a pharmaceutical product, whether or not considered related to the product. An AE can therefore be any unfavourable and unintended sign (including an abnormal laboratory finding, for example), symptom, or disease (new or exacerbated) temporally associated with the use of a product.

Treatment-emergent adverse events (TEAEs)

Any AE with an onset date on or after the study drug start date and no later than 30 days after last dose of study drug, or any worsening of any AE on or after the study drug start date.

Serious adverse events (SAEs)

An SAE is any AE that:

- Results in death.
- Is life-threatening. (Note: The term 'life-threatening' in the definition of 'serious' refers to an event in which the subject was at risk of death at the time of the event; it does not refer to an event that hypothetically might have caused death if it were more severe).
- Requires inpatient hospitalization or prolongation of existing hospitalization.
- Results in persistent or significant disability/incapacity.
- Is a congenital anomaly/birth defect.

• Is an important medical event. Important medical events that may not result in death, be life-threatening, or require hospitalization may be considered an SAE when, based upon appropriate medical judgment, they may jeopardize the patient and may require medical or surgical intervention to prevent one of the outcomes listed in this definition.

Adverse drug reaction (ADR)

An ADR is defined as a response to a medicinal product which is noxious and unintended. Response in this context means that a causal relationship between a medicinal product and an AE is at least a reasonable possibility, i.e., the relationship cannot be ruled out.

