#### 5.3.3.11 Proportion of participants who experienced TEAE and AESI

A treatment-emergent adverse event (TEAE) is defined as an AE that begins or that worsens in severity after at least one dose of osilodrostat has been administered. The start date of adverse events will be compared with date of first dose of osilodrostat and the date of the earlier of loss to follow-up, death, the end of the retrospective follow-up period or treatment discontinuation occurs, whichever is earlier.

TEAE will be coded according to the latest Medical Dictionary for Regulatory Activities (MedDRA) terms and summarized by MedDRA System Organ Class (SOC) and Preferred Term.

Adverse Events of Special Interest (AESI) will be defined as following AEs:

- Adrenal hormone precursor accumulation-related AEs
- Hypocortisolism-related AEs
- Pituitary tumour enlargement-related AEs
- Arrhythmogenic potential and QT prolongation AEs

All AEs will be assessed according to incidence, grade, causality, outcome, action taken and seriousness. The details are provided in the safety analysis section 5.10.1 below.

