# 5.9 Safety Analysis

#### 5.9.1 Adverse Events

All AEs, whether they are serious/non-serious, related/unrelated, and all "special situations" reported in participants' charts within the data collection period should be collected. All AEs will be assessed according to incidence, grade, causality, outcome, action taken and seriousness.

TEAE and AESI were defined in section 5.3.3.5

An overview of adverse events will summarize the percentage of participants experiencing deaths, SAEs, AE reported as reason for discontinuation, TEAEs, and AEs possibly related to study drug.

The frequency and percentage of participants with following will be summarized using MedDRA preferred Term nested within SOC.

- TEAE
- TEAE by maximum severity
- TEAEs related to osilodrostat
- TEAE leading to osilodrostat dose interruption/adjustment
- TEAEs leading to study discontinuation
- SAEs including death
- SAEs by maximum severity
- SAEs related to osilodrostat
- Deaths
- AE of Special Interests (AESIs)

Project Document Version No.: 4.0; Document Effective Date: 30 October 2023

CONFIDENTIAL

RECORDATI AG, Rare Diseases Branch LCI699-RECAG-NI-0596

Statistical Analysis Plan

Adverse event summaries will be ordered in terms of decreasing frequency for SOC, and PT within SOC. For incidence counts, each participant will be counted only once within each Preferred Term and within each SOC. Percentages will be based on the number of participants in safety population. For events that are gender-specific, the denominator and computation of the percentage will include only participants from the given gender.

By-participant listings of all adverse events (including non-treatment-emergent events) recorded on the CRF, all TEATs, TEAEs leading to study discontinuation, SAEs including death, and deaths during the treatment period will be presented by participant, visit, preferred term, severity, and relationship to the study drug.

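### The SAP's rule for treatment-emergent adverse events omits the protocol's 30 days after last dose, and the change is not recorded

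*SAP*

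**What the plan says.** Protocol section 10.1 defines a treatment-emergent adverse event (TEAE) in two clauses. New events need "an onset date on or after the study drug start date and no later than 30 days after last dose of study drug". The second clause adds "or any worsening of any AE on or after the study drug start date" and gives no end.

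Protocol section 8.7.9 sets the period for the TEAE incidence tables. It closes at the earliest of loss to follow-up, death, end of retrospective follow-up "or treatment discontinuation), SAEs and TEAEs by severity grade and relationship to study drug will be provided".

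SAP section 5.3.3.11 first defines a TEAE as an event that begins or worsens after at least one dose, with no end date. It then compares event start dates with the first dose and with "the date of the earlier of loss to follow-up, death, the end of the retrospective follow-up period or treatment discontinuation occurs, whichever is earlier". It does not say what the comparison decides. The 30-day period appears nowhere in the SAP.

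Protocol section 8.7 requires changes of analysis method that fall short of an amendment to be described and justified in the final SAP. SAP section 5.13 says that the SAP carries out the protocol's planned analyses plus some related additions, and lists no change to the TEAE definition.

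On collection, protocol section 8.1 runs follow-up "until the earlier of loss to follow-up, death, the end of the retrospective follow-up period or treatment discontinuation occurs", and a footnote to its Table 2 says "End of data collection may be due to earlier of loss-to-follow-up, death, end of retrospective follow-up period or treatment discontinuation". SAP section 3 repeats both. SAP section 5.9.1 says that adverse events reported in participants' "charts within the data collection period should be collected".

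**The concern.** The proportion of patients with a TEAE or an adverse event of special interest (AESI) is a named secondary endpoint (protocol Table 1, SAP section 3.6.2) in a study meant to support a US label expansion. If the SAP is programmed as written, the TEAE tables will not show what the protocol defined, and a reader of the report could not tell.

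Patients treated briefly are the most exposed, because 30 days is long relative to their time on drug. SAP sections 3.5 and 5.10 plan adverse event and AESI tables for patients treated for less than 12 weeks before surgery.

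The AESI tables carry a related uncertainty. The last sentence of protocol section 8.7.9 limits the AESI summary to treatment-emergent events; the SAP's table list in section 5.9.1 does not repeat the limit.

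**Working it through.** The plan gives no figure to reproduce, so the check applies each rule to the same events.

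1. Inputs. First dose is day 0. Last dose is day 84 (assumed, and taken as the discontinuation date). The protocol window for new events closes at 84 + 30 = day 114. The upper-bound reading of the SAP closes at day 84. The open-ended reading does not close. A worsening is assumed to be recorded with its own start date, which the documents do not say.

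| Event | Protocol 10.1 | SAP, upper bound | SAP, open-ended |
|---|---|---|---|
| New, days 0 to 84 | TEAE | TEAE | TEAE |
| New, days 85 to 114 | TEAE | not counted | TEAE |
| New, day 115 or later | not counted | not counted | TEAE |
| Worsening after day 84 | TEAE | not counted | TEAE |

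2. For new events, the upper-bound reading is narrower than 10.1 and the open-ended reading is wider. On worsening alone, the open-ended reading agrees with 10.1, because 10.1 itself sets no end. The 8.7.9 table period coincides with the upper-bound reading.

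3. What is observed. If abstraction stopped at day 84, the last three rows are empty and the three rules give the same counts; the events are then absent from the data rather than removed by the SAP. The documents allow collection to end at discontinuation but do not say that it always did. SAP sections 3.3 and 5.9.5 provide for records that run past a change to 0 mg, without saying how often.

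4. Patient-level effect. The overall endpoint counts patients, so someone with a TEAE on treatment stays in the overall proportion whatever happens in the tail. That patient can still change a preferred-term or organ-class row. With about 100 patients, each one whose only qualifying event lies in a disputed interval moves the proportion by 1/100, or 1 percentage point: down under the upper-bound reading, up under the open-ended one. One, five or ten such patients (assumed) would mean 1, 5 or 10 points. The documents give no actual number.

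5. Last dose. SAP section 5.9.5 reports a high rate of missing end-of-treatment dates and gives two imputations. Approach A, which lists the same end-of-study reasons as the on-treatment rule in section 3.3, leaves the date missing for reasons outside its list; loss to follow-up is not on it. Approach B uses the end-of-study date where no discontinuation date is available and the dose was not changed to 0 mg. Neither is tied to the TEAE window.

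**The case against.** The strongest reply is that the SAP is clear enough. An end date in a comparison of start dates has one natural use, as an upper bound, and the result matches the protocol's own table period. Since follow-up ends at discontinuation by design, the tail may be largely uncollected, and a discontinuation cut fits the data better than a window built on last-dose dates that are often missing. Much of this stands. The upper bound is the better reading, and keeping it would be defensible if it were declared. It is still not the 10.1 definition, and the departure is not recorded.

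A reader might infer that the protocol holds two rival TEAE definitions. It does not: section 8.7.9 sets a tabulation period and does not define the term. A reader might also infer that nothing bears on which text governs. Protocol section 8.7 and SAP section 5.13 together suggest that 10.1 stands unless a change is declared. But neither says so explicitly, and 5.3.3.11 reads otherwise.

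The protocol window has costs of its own. Post-stop observation will be uneven across patients, and in the surgery subgroup the 30 days may include post-operative events. Protocol section 6 notes that bilateral adrenalectomy causes permanent adrenal insufficiency, so some of those events could be classed as hypocortisolism AESIs.

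**Conclusion.** The point holds as an undeclared departure from the protocol's TEAE definition. Following SAP section 5.3.3.11 under either reading does not produce the new-onset window in protocol 10.1, and SAP 5.13 is silent where protocol 8.7 calls for a description and justification.

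Its reach is limited to patients who stop osilodrostat and have events abstracted afterwards. The primary endpoint is unaffected. For abstracted events, so are the SAE and death summaries, which the SAP does not restrict to treatment-emergent events.

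A reader might infer a large loss of events from window lengths. If all 30 days are observed, the share of the window cut is 30/(28 + 30) = 51.7% after 4 weeks on drug and 30/(84 + 30) = 26.3% after 12 weeks. Patients "will be followed retrospectively for up to 36 months after initiating osilodrostat", about 1,096 days, so the share falls to 30/1,096 = 2.7% for someone who stops 30 days before that cap. These are shares of calendar time that assume a fully abstracted tail; they measure neither events nor the proportion of patients affected. The opposite inference, that rates would barely move, has no support either. Size and direction depend on the unstated number of post-stop events and on which reading is programmed.

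**What to change.** In SAP section 5.3.3.11, replace the date comparison with one window: onset from first dose to 30 days after last dose, as in protocol 10.1, truncated at the last date of observation. State the end that applies to worsening events, which 10.1 leaves open.

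Name the existing rule that sets last dose for this window (section 3.3 with 5.9.5 approach A, or approach B). Use the last date of observation where that rule leaves the date missing.

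Record in section 5.13 how the window relates to the table period in protocol 8.7.9. If the sponsor prefers the discontinuation cut, record and justify it there as a departure from 10.1, and also tabulate TEAEs in the 30-day window where they were recorded.

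Apply the treatment-emergent limit in protocol 8.7.9 to the AESI summary.

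In the report, say whether events were abstracted after last dose. Give as limitations the uneven observation of the tail, the many window ends that rest on imputed dates, and the possible inclusion of post-operative events in the short-term surgery subgroup.

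Two clerical cross-references can be corrected in the same edit: section 5.9.1 points to 5.3.3.5 (dose change) instead of 5.3.3.11, and 5.3.3.11 points to 5.10.1 instead of 5.9.1.

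The cost is SAP wording, the matching programming, and a few lines in the report. No renewed chart review is needed.

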#### 5.3.4 Exploratory endpoint analysis

For late night salivary cortisol observed values at baseline and changes from baseline to Week 4, 8,12, 18, 24, 36 and to every 12 weeks until the earlier of loss to follow-up, death, or the end of the retrospective follow-up period or treatment discontinuation, descriptive summaries will be provided for every visit at which the cortisol markers are collected. Where applicable, proportion of participants with normal and/abnormal late night salivary cortisol will also be provided at every visit.

A participant level listing will be provided with all required details as per the eCRF.

#### 5.3.5 Sensitivity Analysis

No formal sensitivity analysis will be performed, although the primary endpoint analysis will be performed on the mITT and On-Treatment populations as well.

#### 5.3.6 Stratified Analysis

Project Document Version No.: 4.0; Document Effective Date: 30 October 2023

CONFIDENTIAL

RECORDATI AG, Rare Diseases Branch LCI699-RECAG-NI-0596

Statistical Analysis Plan

For the potential confounding identification objective, participants will be stratified if they received or did not receive other therapies for Cushing's syndrome (regardless of the type of therapy) from start of study treatment to week 12. The statistical null hypothesis states that the response rates at the end of the 12-week period (i.e., at Week 12) are the same between the participants with/without non-study CS treatment. To test this hypothesis, a Cochran-Mantel-Haenszel (CMH) exact test by non-study CS treatment (yes/no) will be performed using the ITT.

If the 2-sided p-value is  $\leq$  0.05, and the odds ratio (non-study CS medication treatment yes vs. no) is > 1, the null hypothesis will be rejected and the response rate at week 12 in the non-study CS treatment yes group will be considered higher than that in the non-study CS medication treatment no group.

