#### Reason for Osilodrostat use

- 1) **Short-term use in preparation for surgery**: Patients who took Osilodrostat for < 12 weeks had a surgical procedure to treat Cushing's syndrome and were not restarted on Osilodrostat.
- 2) Chronic use: All other patients

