#### 5.3.2 Analysis of the Primary Endpoint

The mean UFC for a participant at any particular visit is collected in the site. If mean UFC is not available at that visit, the mean UFC will be computed based on two or more individual 24hr UFC specimens at that visit. If there are only one individual 24hr UFC specimen available at that visit, then this one individual 24hr UFC specimen will be considered as mean UFC with the acknowledgement of clinical practice in France where one 24 hours UFC can inform on clinical decision.

The primary endpoint is the number and proportion of participants with mUFC ≤ ULN at 12 weeks will be summarized descriptively along with associated 95% CI. The participants who discontinued treatment prior to 12 weeks for any reason or were lost-to-follow up will be considered non-responders for the primary endpoint. The participants who started treatment with osilodrostat less than 12 weeks prior to the end of the abstraction period and are still treated with osilodrostat at the end of the abstraction period will be excluded from the analysis.

Project Document Version No.: 4.0; Document Effective Date: 30 October 2023

CONFIDENTIAL

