#### 5.8 Prior and Concomitant Medications

The prior and concomitant systemic therapy, radiotherapy and surgical therapy will be summarized in similar manner as described.

Medication start and stop dates will be compared to the date of first dose of osilodrostat to allow medications to be classified as either Prior only, both Prior and Concomitant, or Concomitant only. Medications starting after the completion/withdrawal date will be listed but will not be classified or summarized.

Medications that start and stop prior to the date of first dose of osilodrostat will be classified as Prior only. If a medication starts before the date of first dose of osilodrostat and stops on or after the date of first dose of osilodrostat, then the medication will be classified as both Prior and Concomitant. Medications will be classified as Concomitant only if they have a start date on or after the date of first dose of osilodrostat.

If medication start and/or stop dates are missing or partial, the dates will be compared as far as possible with the date of first dose of osilodrostat (see section 5.11.2). Medications will be assumed to be Concomitant only, unless there is clear evidence (through comparison of partial dates) to suggest that the medication started prior to the first dose of osilodrostat. If there is clear evidence, such as an ongoing medical history with the same indication, to suggest that the medication started prior to first dose of osilodrostat and with no stop date, the medication will be assumed to be both Prior and Concomitant. If there is clear evidence to suggest that the medication stopped prior to first dose of osilodrostat, the medication will be assumed to be Prior only.

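### The ITT check for confounding by other Cushing's therapy (SAP 5.3.6) counts therapy given after osilodrostat was stopped, in patients who are non-responders by rule, so it can mask real confounding

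*SAP*

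**What the plan says.** SAP 5.3.6 states its aim as identifying potential confounding. Patients are split by whether they received "other therapies for Cushing's syndrome (regardless of the type of therapy) from start of study treatment to week 12". A "Cochran-Mantel-Haenszel (CMH) exact test by non-study CS treatment (yes/no) will be performed using the ITT". The decision rule is one-directional: if the two-sided p-value is at most 0.05 "and the odds ratio (non-study CS medication treatment yes vs. no) is > 1, the null hypothesis will be rejected" and the *yes* group is declared to respond better. That sentence speaks of medication, whereas the stratum definition covers any type of therapy.

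In the ITT, SAP 5.3.2 provides that "participants who discontinued treatment prior to 12 weeks for any reason or were lost-to-follow up will be considered non-responders for the primary endpoint".

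SAP 3.5 defines a subgroup for short-term use before surgery: "Patients who took Osilodrostat for < 12 weeks had a surgical procedure to treat Cushing's syndrome and were not restarted on Osilodrostat".

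Protocol 8.7.12 has the same two strata without a time window and asks for a difference in proportions with a 95% CI. The amendment rationale for that section says the analysis was added to deal with patients whose other Cushing's therapies might confound the osilodrostat results.

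**The concern.** The exposure is defined by calendar time since first dose. It does not depend on whether the patient was on osilodrostat, or on when the mUFC sample was taken. Two rules then meet in the same patient. Someone who takes osilodrostat for six weeks and has an adrenalectomy in week 10 is exposed under 5.3.6 and a non-responder under 5.3.2. The operation came after osilodrostat and cannot have raised a response attributed to it, so this patient carries no information on the question asked. The effect is only to pull the *yes* rate down. Because the rule concludes only when the odds ratio exceeds 1, that pull is always towards finding nothing.

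The timing also fails at the other end. The Week 12 window is ±4 weeks (SAP Table 1), so a therapy added in week 13 and present at a week 15 sample counts as *no*.

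At stake is the reliability of the one formal ITT test of whether other therapy inflates the primary result, in a study intended to support a label expansion.

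**Working it through.** **Inputs from the documents.** ITT population; flag if p ≤ 0.05 and OR > 1 (SAP 5.3.6); early stoppers are non-responders (SAP 5.3.2); about 100 patients (SAP 5.12). The documents give no stratum sizes, response rates or power for this analysis, so there is no figure to reproduce.

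**Assumptions.** N = 100; 20 patients on concurrent therapy responding at 85%; other on-drug patients responding at 60%; *s* patients treated only after stopping (all in *yes*, all non-responders); *d* early stoppers with no other therapy (all in *no*, all non-responders). The remaining on-drug patients number 100 − 20 − *s* − *d*. A CMH exact test on a single 2×2 table is treated as Fisher's exact test. Flag probabilities come from enumerating the binomial outcomes.

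**Step 1, on-drug contrast, s = 10, d = 0.** 17/20 vs 42/70. OR = (17 × 28)/(3 × 42) = 476/126 = 3.78, p = 0.060.

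**Step 2, as written.** The 10 post-stop patients join *yes*: 17/30 (56.7%) vs 42/70 (60.0%). OR = (17 × 28)/(13 × 42) = 476/546 = 0.87, p = 0.83.

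**Step 3, varying s with d = 0.**

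| s | *yes* | *no* | OR | Chance of a flag |
|---|---|---|---|---|
| 0 | 17/20 | 48/80 | 3.78 | 54% |
| 5 | 17/25 | 45/75 | 1.42 | 3% |
| 10 | 17/30 | 42/70 | 0.87 | below 0.1% |
| 15 | 17/35 | 39/65 | 0.63 | about 0% |
| 20 | 17/40 | 36/60 | 0.49 | about 0% |

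If the post-stop patients are left out of the contrast, the chance of a flag is 51% at s = 5 (20 vs 75 patients) and 52% at s = 10 (20 vs 70). The loss therefore comes from where these patients are placed and hardly at all from the smaller sample.

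**Step 4, the opposite pull.** Early stoppers with no other therapy lower the *no* rate. With d = 10 and s = 0 the table is 17/20 vs 42/80, OR = (17 × 38)/(3 × 42) = 646/126 = 5.13, p = 0.010, and the chance of a flag rises to 81%. Adding s = 10 brings it to 1%. With 30 concurrent users the same step goes from 92% to 18%.

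**Step 5, why moving post-stop patients to *no* does not work.** That gives the 17/20 vs 42/80 table of Step 4, which overshoots the on-drug value of 3.78. A second set of assumed counts shows the same: 15/20 vs 40/60 on drug gives OR 1.50 (p = 0.58), but with 20 early stoppers added to *no* it is 15/20 vs 40/80, OR 3.00 (p = 0.049). In that layout, with no on-drug difference at all (66.7% in both groups), the SAP rule flags confounding 24% of the time (19% at 60% response, 31% at 75%). Without early stoppers, and with 60% response in both groups, it does so about 2% of the time.

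**The case against.** **Surgery may not count.** The decision sentence refers to medication, and a drugs-only reading would remove surgery from *yes*. But the stratum definition says the opposite, so the section contradicts itself and has to be reconciled in any case.

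**Post-stop drugs may not be captured.** Follow-up ends at treatment discontinuation if that comes first (SAP 3), and drugs started after completion or withdrawal are not classified (SAP 5.8). This stands in part. The SAP allows a dose of 0 mg before the end of study (SAP 3.3 and 5.9.5), so a gap can exist, but that does not show that replacement drugs were recorded in it. Surgery is the firmer case, since the SAP 3.5 subgroup depends on identifying patients who "had a surgical procedure to treat Cushing's syndrome and were not restarted on Osilodrostat".

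**Other analyses cover it.** The primary endpoint is repeated in the mITT and On-Treatment populations (SAP 5.3.5), and mUFC response is reported by treatment-naive, switch and combination groups in both (SAP 3.5, 5.10). The On-Treatment population removes post-stop patients, and the mITT excludes those whose intervention prevented a Week 12 mUFC. This is real mitigation, so a reader should not infer that the plan ignores combination therapy elsewhere. It is partial because the 5.3.6 test is run on the ITT only.

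**Sign reversal.** A reader might infer that the plan could report confounding in the wrong direction. The SAP does not support that: its rule draws no conclusion when the odds ratio is below 1. The reversal is mainly in the point estimate. In the Step 2 setting a significant odds ratio below 1 occurs about 1% of the time.

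**Direct switches.** A reader might also object that a drug stopped on the first-dose day counts as exposure, because under SAP 5.8 a drug that "stops on or after the date of first dose of osilodrostat, then the medication will be classified as both Prior and Concomitant". That is an edge case. Section 5.3.6 does not invoke those labels, and Protocol section 6 describes mitotane as having a long half-life, so it cannot be assumed that such a patient's Week 12 sample reflects osilodrostat alone.

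**Conclusion.** The point holds as a masking problem. As written, the ITT test mixes therapy that could have raised the Week 12 response with therapy that replaced osilodrostat in patients already fixed as failures. Under the assumed 85% vs 60% response with 20 concurrent users, five post-stop patients in 100 are enough to take the chance of a flag from about 50% to 3%, and ten move the odds ratio from 3.78 to 0.87. The true number of such patients is not in the documents. The net bias also depends on how many early stoppers had no other therapy, because they push the odds ratio upwards. With ten of them in *no*, the odds ratio first falls below 1 at 14 post-stop patients (20 concurrent users) or 25 (30 users), against 9 and 13 with none.

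The primary estimate is unchanged, and the study is otherwise descriptive. The change should be made because this analysis was added specifically to detect confounding by other therapy.

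**What to change.** In SAP 5.3.6:

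1. Define *yes* as non-study Cushing's therapy that overlaps osilodrostat treatment and was given up to the date of the mUFC sample used for Week 12, which may fall after week 12 under the ±4-week window.
2. Run the yes/no contrast in ITT patients still on osilodrostat at that sample, leaving out anyone who stopped before week 12.
3. Report the patients who stopped before week 12 in a separate row, split by whether they then had surgery or another Cushing's therapy, and in neither arm of the contrast. State where patients who stop between week 12 and a later sample, or who have no Week 12 sample, are counted.
4. Keep the existing ITT version as a secondary display.
5. Reconcile the any-therapy wording of the stratum with the medication wording of the decision rule.

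The cost is a paragraph of SAP text and one derived flag from treatment, medication and sample dates. Post-stop therapy may be incompletely recorded, so the split in item 3 should be labelled as such. The statistical price is a smaller sample for the contrast and a result conditional on staying on treatment, which is why the ITT version stays beside it.
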